#### **11.4 Treatment Assignment**

All shoulders will be treated with PyroTITAN™ HRA Shoulder prosthesis.

#### **11.5 Interim Analysis**

Data will be reviewed for safety in an ongoing manner, according to standard formal procedures at Ascension Orthopedics. No interim analysis *per se* is planned; but it is anticipated that a number of outcomes will be followed through time; for example, surgical technique, and return to function.

#### **11.6 Data Analysis**

Although this study is exploratory in nature, for many investigations the success of the implant will be a primary endpoint.

#### **11.7 Primary Endpoint**

Clinical requirements for success will be evaluated at 24, 60 and 120 months:

- Device remains implanted
- Absence of device-related complications requiring surgical replacement, removal, or augmentation of components
- Freedom from chronic dislocation

#### **11.8 Secondary Endpoint**

Radiographic and MRI requirements for success at the different time points:

- No evidence of device failure, specifically progressive migration or implant loosening
- Anatomic alignment is a criterion that may be included in the definition of success in some investigations

Clinical outcomes measures at the different time points.

### **11.9 Other Endpoints**

The following will be analyzed at the end of the trial:

Adverse Events including, but not limited to:

- Infection
- Loss of fixation
- Breakage
- Dislocations
- Revisions

Data will be entered, verified and validated using a computer database system. Both the data management and statistical analysis will be performed by Ascension Orthopedics, Inc. Descriptive statistics of patient demographic details will be calculated over all patients. Pre-operative values of outcome variables will be compared to postoperative values at various time points. For interval level data, t-tests will be used; for ordinal level data (ranked data) the Wilcoxon matched-pairs signed-ranks test will be employed, and chi-square or Fisher's exact tests will be used for categorical data. Correlation coefficients may also be employed to determine whether preoperative variables are related to outcome variables.

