### **6.1 Pre-Operative Management**

Pre-admission testing may be conducted to satisfy the medical/surgical requirements of each Investigator, hospital or institution participating in the study. Such testing is not intended to determine comparability of the study device and will, therefore, not be documented by the Sponsor. The investigators will obtain the clinical information and record it in the medical chart. Data collected will address the following: demographic information, age, sex, date of birth, patient reported height and weight, hand dominance, side of injury, history of present illness, diagnosis, mechanism of injury, smoking and diabetes status, history of fracture and x-ray availability (all of which are standard data collected during routine history taking). Patients will be asked to verify the information collected from the medical chart and update information as appropriate at designated post-operative visits. Prior to surgery, the following procedures must be completed for each enrolled subject to satisfy study requirements:

1. Executed Informed Patient Consent
2. Verification of all inclusion and exclusion criteria
3. Subject medical history review
4. Radiographic (X-ray and MRI) evaluation
5. Clinical evaluation
6. Subject self-assessments

As part of the pre-operative assessment of each study subject, the investigator will complete the Constant Score CRF based on source documentation. The Subjects will obtain radiographs, complete the WOOS, EQ-5D, the VAS Scales, ASES Shoulder Evaluation, and update Health History Profile. The center will submit x-rays and MRI's for independent evaluation. All data will be compared with the follow-up data obtained at each study interval.

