# 7 STATISTICAL ANALYSIS

## 7.1 General

Smith + Nephew's Global Biostatistics group will conduct the statistical analysis for this study. Unless otherwise stated, all significance tests and hypothesis testing will be two-sided, performed at the 5% significance level. Resulting p-values will be quoted and 95% two-sided confidence intervals will be generated where appropriate. All p-values will be rounded to three decimal places, p-values less than 0.001 will be presented as '<0.001' in all tables.

Where data summaries are specified, categorical and ordinal variables will be summarized with frequencies and percentages. Continuous variables will be summarized with the following summary statistics: number of observations, mean, median, standard deviation, minimum and maximum values. All analyses will be performed in SAS 9.4 (or later).

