## 7.14 Changes in Analysis Methods Specified in the Protocol

- The 5-year interim analysis was not specified in the protocol however it has been added to allow for the 2 and 5 year data to be published.

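### Protocol 11.9 applies independent-sample tests (chi-square, Fisher) to categorical outcomes compared before and after surgery in the same patients

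*Protocol*

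**What the plan says.** Protocol 11.9 states the comparison first: "Pre-operative values of outcome variables will be compared to postoperative values at various time points". It then assigns a test to each data type:

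- Interval: "For interval level data, t-tests will be used", with pairing not mentioned.
- Ordinal: "the Wilcoxon matched-pairs signed-ranks test will be employed", which is explicitly paired.
- Categorical: chi-square or Fisher's "exact tests will be used for categorical data", with no paired alternative.

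There is one treatment group. Protocol 11.4 says "All shoulders will be treated with PyroTITAN™ HRA Shoulder prosthesis", and Protocol 6.1 says of the pre-operative assessments that "All data will be compared with the follow-up data obtained at each study interval". The pre- and post-operative values therefore come from the same patients.

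The SAP contains no chi-square, Fisher, McNemar or marginal-homogeneity test. SAP 7.10 uses paired t-tests for ASES, VAS pain, WOOS and Constant-Murley, with a Wilcoxon signed-rank fallback for all of these except VAS pain. It uses a repeated-measures model for the EQ-5D index and EQ VAS. It only tabulates the EQ-5D dimension responses, and it passes the radiographic analysis to a vendor under a separate SAP.

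**The concern.** A two-sample chi-square or Fisher test on the pre- and post-operative proportions treats 52 patients measured twice as 104 different patients. The variance it uses for the difference omits the within-patient covariance. If the two measurements are positively correlated, that variance is too large, so the test rejects too rarely and loses power. If they are negatively correlated, it is too small and the test rejects too often. Applying chi-square to the cross-table of pre by post is no remedy, because that tests whether the two measurements are associated, not whether the proportion has changed.

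The outcomes exposed are radiographic. Protocol 4.0 makes the pre/post difference in radiographic alignment part of the study's purpose. The protocol summary and SAP 5.2 both compare radiographic performance with pre-treatment results. Protocol 6.4 has alignment, glenoid condition and joint congruity read at every imaging visit, including the pre-operative one. If any of these is scored in categories, Protocol 11.9 is the only test rule in the two documents that covers it.

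**Working it through.** **Is there a figure to reproduce?** No. Neither document gives a sample size, power or expected proportion for a categorical pre/post test, so the size of the effect can only be illustrated under assumptions.

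**Inputs from the documents**

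- Number of pairs: 52, the protocol's expected ten-year count for the original cohort (Protocol 11.3: 150 × 0.9^10 = 52.3). 150, the full original cohort, is used as a second case.
- Level: SAP 7.1, "Unless otherwise stated, all significance tests and hypothesis testing will be two-sided, performed at the 5% significance level".

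**Assumed inputs (not in the documents)**

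- Proportions: 50% before and after under the null; 50% to 65% under the alternative.
- Within-patient correlation φ: 0.3, 0.5 and 0.7, with -0.2 as a contrast.

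**Step 1: direction, by formula.** For paired proportions p₁ and p₂ on n patients,

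Var(p̂₂ − p̂₁) = [p₁(1−p₁) + p₂(1−p₂) − 2φ√(p₁(1−p₁)p₂(1−p₂))] / n.

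The unpaired test drops the last term. Under the null, p₁ = p₂, so the true variance is (1 − φ) times the variance that chi-square uses. In large samples, rejecting at 1.96 on the wrong scale means rejecting at 1.96/√(1 − φ) on the right one:

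| φ | 1.96/√(1−φ) | Approximate true size |
|---|---|---|
| -0.2 | 1.79 | 7.4% |
| 0.3 | 2.34 | 1.9% |
| 0.5 | 2.77 | 0.6% |
| 0.7 | 3.58 | 0.03% |

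**Step 2: simulation at realistic n.** Paired binary data were drawn from the multinomial with P(both positive) = p₁p₂ + φ√(p₁(1−p₁)p₂(1−p₂)). There were 20,000 replicates per setting (4,000 for Fisher).

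Type I error, n = 52, nominal 5%:

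| φ | Chi-square | Fisher | McNemar, asymptotic | McNemar, exact |
|---|---|---|---|---|
| -0.2 | 8.8% | 6.0% | 5.2% | 3.0% |
| 0.3 | 2.5% | 1.3% | 5.2% | 2.9% |
| 0.5 | 0.9% | 0.4% | 4.5% | 2.7% |
| 0.7 | 0.1% | 0.0% | 4.4% | 1.9% |

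Power for 50% to 65%, n = 52:

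| φ | Chi-square | Fisher | McNemar, asymptotic | McNemar, exact |
|---|---|---|---|---|
| 0.3 | 34% | 25% | 46% | 36% |
| 0.5 | 31% | 22% | 57% | 48% |
| 0.7 | 26% | 16% | 86% | 74% |

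At n = 150 and φ = 0.5, chi-square has a type I error of 0.8% and power of 84%, against 5.1% and 97% for asymptotic McNemar. The miscalibration does not shrink as n grows, although at n = 150 its cost in power is smaller.

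**Step 3: which analyses are reached?**

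- Primary endpoint (implant retention, complications, chronic dislocation): no pre-operative value, so not affected.
- Adverse events, migration, loosening, radiolucency around the device: nothing to compare before implantation.
- ASES, WOOS, Constant-Murley, VAS pain: paired tests in SAP 7.10.
- EQ-5D dimensions: summarised only.
- Satisfaction: no baseline (SAP 7.10).
- Range of motion: summarised as continuous (SAP 7.11).
- Radiographic features that exist before surgery, such as alignment: compared with pre-treatment, with the method left to a plan not seen here. These are the only outcomes left.

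**The case against.** The best case against the point is that no scheduled analysis uses the faulty rule. The 2023 SAP sets out the analysis methods for this protocol version, contains no chi-square or Fisher test, and makes its t-tests paired where the protocol did not say so. The study calls itself exploratory, and with positive correlation the error is on the conservative side. Most of this stands and limits the point to a minor one. It does not cover the radiographic outcomes, which the SAP hands elsewhere without stating a test.

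Two softer readings of Protocol 11.9 do not hold. Chi-square might loosely include McNemar's statistic, but Fisher's exact test, named beside it, cannot. The tests might be meant for comparing the original and new cohorts, but the sentence directly follows the pre/post comparison and mentions no cohorts.

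A reader might also infer two stronger things that the documents do not support:

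- *That the wrong test will be applied to the EQ-5D dimensions.* These have three ordered levels. Protocol 11.9 would send ordinal data to the matched-pairs Wilcoxon test, and SAP 7.10 only summarises them.
- *That the rule must still be in force because SAP 7.14 does not withdraw it.* That section lists one change, "The 5-year interim analysis was not specified in the protocol". It also omits the move from t-tests to a repeated-measures ANCOVA for the EQ-5D index and EQ VAS, so it is not a complete list. Its silence shows neither that the rule was kept nor that it was dropped.

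**Conclusion.** The point holds for the protocol's wording: 11.9 prescribes independent-sample tests for paired categorical data. Its practical reach is narrow. It concerns categorical radiographic outcomes compared with pre-treatment, and only if they are tested and the separate radiographic plan follows the protocol. Nothing in the primary analysis, the sample size or the clinical scores depends on it.

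The direction follows from the variance formula. The size rests on assumed proportions and correlations. At 52 pairs and positive correlation, the assumed settings put the loss against asymptotic McNemar at 12 percentage points of power (46 − 34) at φ = 0.3 and 60 (86 − 26) at φ = 0.7. Against exact McNemar it is 2 points (36 − 34) at φ = 0.3. It would be wrong to call the unpaired test simply safe, since a negative correlation makes it liberal. The 52 pairs may also be generous for imaging, because Protocol 11.3 expects ten-year radiographs on only about 35 of those shoulders.

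**What to change.** For any within-patient pre/post comparison of categorical data, replace chi-square and Fisher by:

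- McNemar's test for binary outcomes, in its exact form when discordant pairs are few;
- Stuart-Maxwell (marginal homogeneity) or Bowker (symmetry) for more than two unordered categories.

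Ordered categories already fall under the protocol's matched-pairs Wilcoxon rule.

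The change can be made in Protocol 11.9, or by an entry in SAP 7.14 together with the same sentence in the radiographic SAP. The second route is cheaper, because Protocol section 20 requires sponsor consent, agreement with the investigators and recording by the ethics boards for a protocol change. If no categorical pre/post test will be run, one line in SAP 7.14 saying that it is dropped is enough.

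No new tests should be added to SAP 7.1 for outcomes that the SAP only summarises. That would create extra significance tests in a plan with no multiplicity adjustment (SAP 7.8). No new data or patients are needed.

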## **12.0 Risk Analysis**

---

Radiographs are a normal part of post-operative follow up and the subject will experience no additional radiation exposure beyond what is clinically necessary. The radiation exposure risk is estimated to be 0.004mSv per follow-up interval with 8 intervals in the study. This is comparable to 36 days exposure to natural background radiation. The radiation exposure risk is based on an X-ray to the upper extremity which has a radiation exposure of 0.001mSv per x-ray. Muscle discomfort and/or shoulder joint pain may occur during the musculoskeletal muscle strength and range of motion testing. The patient will be informed that rest and ice should be applied. Additional concerns should be directed towards the treating surgeon for consultation. PyroTITAN™ HRA Shoulder prosthesis risks,

**Confidential**

Protocol Date: May 27, 2013

Amendment 1

Revision 2

**Ascension Orthopedics**

CP-HRA-002

that are no different from other prosthesis, include infection, failure of prosthesis, implant loosening, or shoulder dislocation and/or subluxation. The patient will be told this during the normal pre-surgical information process and sign an Informed Consent related to the surgical procedure acknowledging this information. Any complications can be treated with conversion to total shoulder arthroplasty, reverse shoulder arthroplasty, or shoulder arthrodesis (fusion).

The benefits of shoulder resurfacing surgery depend upon each patient. Benefits usually include a conservation of humeral bone, reduction or relief of pain, restoration or improvement in range of motion and mobility, correction or improvement of disfiguring deformity and an improvement in the patient's quality of life. Participation in this study may benefit society as well as provide valuable information to the orthopaedic community other doctors and help them make informed decisions about the kind of shoulder replacement components most likely to benefit their patients. The patients will benefit by becoming better informed of the status of their shoulder or injury. They will have added contact with their surgeon and his or her staff. The patient will also be informed of the status of the Pyro-Titan Resurfacing Shoulder prosthesis during their follow-up examination assessment visits. Results of this study will provide information about the effect of Pyro-Titan Resurfacing Shoulder prosthesis on the functional outcomes experienced by the subjects post shoulder arthroplasty.

Minimal risks are associated with this study. Subjects may experience infection, failure of prosthesis, glenoid wear, implant loosening, or dislocation post PyroTITAN™ HRA Shoulder prosthesis implant. The risks of harm anticipated in the proposed research are not greater, considering probability and magnitude of those ordinarily encountered in shoulder arthroplasty or during the performance of routine physical and psychological examinations or tests. The patient may or will experience changes in function, pain, and satisfaction levels of activities of daily living. The other alternative is to continue with their current levels of satisfaction, function and pain as related to the shoulder arthritis.

Any surgical procedure poses a potential risk and the procedures undertaken as part of this clinical investigation are no exception. There are known risks associated with the method

**Confidential**

Protocol Date: May 27, 2013

Amendment 1

Revision 2

**Ascension Orthopedics**

CP-HRA-002

of anesthesia (general, epidural, spinal). Separate consent forms will be presented to subjects outlining the risks of shoulder surgery and anesthesia. In addition to these there are risks associated with a surgical procedure that involves a device, including the following: damage to nervous and vascular tissue, infection, long term swelling, fracture of bone surrounding the device, loosening, dislocation or fracture of the device, hemorrhage, decrease in range of motion or mobility deformity, allergic reaction to the device and failure of the device to be incorporated into the body. A complication may require revision surgery. Very rarely a complication may prove fatal. This clinical trial of the CE marked (November 30th, 2009)PyroTITAN™ HRA Shoulder prosthesis, used according to this protocol and labeling indications, poses no additional risks over those normally associated with shoulder resurfacing arthroplasty.

## **13.0 Device Descriptions**

---

The Ascension® PyroTITAN™ HRA device is an anatomically designed, semi-constrained, monolithic device designed for resurfacing of the humeral head (hemi-shoulder). The system is designed for non-cemented (i.e. press-fit) fixation. Each device is boxed individually and delivered sterile for single use. The system incorporates twelve anatomically designed sizes. Head sizes are identified using width and height (in millimeters) and are as follows: 38/14, 41/15, 41/18, 44/16, 44/19, 47/17, 47/20, 50/18, 50/21, 53/19, 53/22 and 56/21. The PyroTITAN™ HRA device incorporates design features for replacing the damaged humeral head bearing surface and restoring normal anatomy with minimal bone resection. The stem is tapered with a cruciform shape to provide rotational as well as axial stability of the seated implant. System instrumentation is designed to offer precise implant preparation. Device components are provided sterile in packaging containing a single component.

**Confidential**

Protocol Date: May 27, 2013  
Amendment 1  
Revision 2

**1 Orthopedics**  
CP-HRA-002

---

## **14.0 Investigator Responsibility**

Prior to the initiation of this clinical investigation, the Clinical Investigator will approve this CIP by signing a research agreement. This signature confirms that the clinical investigation will be performed in compliance with the CIP.

All Investigators are responsible for maintaining a complete case history for each Subject. This case history must be adequately detailed to cover all data points on the Case Report Forms. Worksheets may be developed and implemented to simplify this process, or it is expected that detailed dictations will be done. The case history is defined as the “source documentation.”

Each Investigator and all personnel from the investigational site will maintain records of all correspondence, electronic, written, and verbal, relating to any aspect of the clinical investigation. The records are maintained in the Investigator’s Regulatory Binder consisting of, but not limited to correspondence with other participating clinical investigators, the reviewing ETHICS BOARD, and the Sponsor. The study monitor will examine the contents of the correspondence file as part of the monitoring visit.

Prior to the investigational site beginning Subject enrollment, the following documents will be fully executed and returned to Ascension Orthopedics by the clinical investigators:

- Curriculum vitae (c.v.)
- Medical license
- Confirmation of ETHICS BOARD Approval
- Clinical Research Agreement
- Investigator Compensation Agreement
- Financial Disclosure

Copies of the Investigator Agreement will be provided by the Sponsor after contracting.

## **14.1 Investigator Regulatory Binder**

Each investigator must maintain an accurate, complete, and current copy of the Investigator Regulatory Binder. Upon receipt of copies of changes or revision updates to the Investigator Regulatory Binder(s) from the Sponsor, the Investigator or designee will add the updated document to the Regulatory Binder and will mark the outdated portion of the Regulatory Binder as “obsolete” by crossing a diagonal line across the page(s) along with date the page was obsoleted and the initials of the person performing the update. The outdated pages will be removed from their current section and filed in the “Obsolete” section. The study monitor will examine the contents of the Investigator Regulatory Binder as part of the monitoring visit.

## **14.2 Case Report Form Completion**

Data will be transposed onto the CRF's or data collection form. Data will be accurately and completely recorded in ink on the CRF's or electronically on the data collection form. Prior to submission to Ascension, any errors on the forms are to be corrected, either crossed out with a single stroke, initialed and dated on the paper form or by verification and reentry of electronic data. Typing correction fluid must not be used. After submission to Ascension, no changes may be made to the data collection form. Instead, a Data Clarification Form (DCF) must be used to document any modifications to a data collection form. The signed, original DCF is submitted to Ascension and a copy is affixed to the original, corresponding CRF. The personal data recorded on all documents will be regarded as confidential. The Clinical Investigator will be responsible for the timing, completeness, and accuracy of the data collection form and will retain a copy of each completed form.

The Investigator's copies of the Investigation, including Consent forms and CRF's should be held for a minimum of fifteen years after the completion of the investigation. In the event the Clinical Investigator retires or moves, the investigator will provide the name and address of the custodian of the study records. Alternatively the custody of the study records may be transferred to the Sponsor with notification to the governing Ethics Board.

**Confidential**

Protocol Date: May 27, 2013  
Amendment 1  
Revision 2

**Ascension Orthopedics**

CP-HRA-002

The subjects' participation in the investigation must be recorded in the Subject's hospital notes. In addition, the Investigator must keep a separate list of all subjects entered into clinical investigation. This list should include the name, date of birth, and subject number.

## **15.0 Institutional Review Board (ETHICS BOARD) Action**

This study is intended to monitor post-market clinical outcomes of the devices described above. The Notified Body has cleared all devices utilized in this evaluation for general use in accordance with printed indications. It is the responsibility of the investigator to submit a copy of the investigational plan and secure approval of the governing ETHICS BOARD for each institution under consideration for the study. If ETHICS BOARD approval is not required, this must be indicated in a signed letter from the governing ETHICS BOARD.

No subjects should be consented or requested to complete a release of medical records until ETHICS BOARD approval has been obtained. It is the responsibility of the investigator to comply with governing ETHICS BOARD requirements including but not limited to reporting adverse events, reporting consent and protocol deviations, submission of periodic reports in a timely manner and any other institutional, state or federal regulations.

